8.6. Data management

The planned analyses will be conducted, by a statistician at the Department of Clinical Epidemiology Aarhus University Hospital, on combined individual-level datasets from all three countries, prepared according to a common data model (CDM) (48). A CDM is a set of uniform datasets, whereby specified parameters include the names and the number of the datasets, full list of variables in each dataset (including all candidate variables for inclusion in estimation of propensity score), and attributes of each variable (including name, type, length, format). The CDM for this study will be developed by the Department of Clinical Epidemiology, Aarhus University Hospital and will consist, at a minimum, of a population file, a diagnosis file (covariates), an endpoint file, and a drug file (exposures and covariates); additional files containing socioeconomic variables may be created.

Each research partner will complete all data management and quality control (cleaning, coding, plausibility checks etc.) required to convert the raw data into the pre-specified CDM. Within each country, the CDM input data files will be linkable on individual level via a

unique study identifier. This identifier will replace the true personal identifier for the purpose of analysis. The completed input dataset will be transferred for analysis to a secure server at Statistics Denmark, where all data will be kept in accordance to the rules and regulations governing protection of personal data. [Figure 5](#) shows an example of a CDM.

Figure 5. An example of files prepared in each country according to a common data model.

The CDM will be detailed in the final SAP. Data will be managed and analysed using SAS software version 9.2 or higher (Cary, North Carolina, US). Investigators in Norway and Sweden will obtain all approvals required for data transfer to Denmark for analysis. All investigators have experience conducting multinational studies using CDM, both in Scandinavian (49, 50) and in other European studies (51).

8.7. Data analysis

All analyses will be conducted on the combined patient-level dataset and on patient-level dataset stratified by country. In the analysis combined across the three countries, country will be used as a cluster variable to account for within-country correlation in the multivariate models.

Detailed methodology for summary and statistical analyses of data collected in this study will be documented in a common SAP, which will be dated, filed and maintained by the MAH. The SAP may modify the plans outlined in the protocol; any major modifications of primary endpoint definitions or their analyses would be reflected in a protocol amendment.

A statistician at the Department of Clinical Epidemiology, Aarhus University Hospital, will write the analytic code and will conduct all analyses within the scope of this protocol, including propensity score estimation, pooled analyses and analyses stratified by country. Full operational definition for each variable, and the analytic strategy, including variables for inclusion in the propensity score models, are described in the SAP.

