8.3.3. Covariates

Baseline characteristics of the study cohorts will be ascertained during the maximum of 5-year baseline before and including the index date (38): age at index date (in groups and as a continuous variable), sex, overall comorbidity (using the Charlson Comorbidity Index (39, 40)), the CHA₂DS₂VASc score, CHADS₂ score, the HAS-BLED score, major bleeding, ischemic stroke, transient ischemic attack (TIA), history of heart failure (HF), cancer, diabetes, hypertension, chronic kidney disease, liver disease, myocardial infarction, alcohol abuse, peripheral arterial disease (PAD), coronary artery disease (CAD), dementia, cancer, and cardioversion. Baseline concomitant medication use will be assessed as history of dispensings for angiotensin converting enzyme (ACE) inhibitors, amiodarone, dronedarone, beta-blockers, H₂-receptor antagonists, proton pump inhibitors, antidiabetics, anti-platelets, statins, aspirin, selective serotonin reuptake inhibitors (SSRIs), and non-steroidal anti-inflammatory drugs (NSAIDs). Socioeconomic characteristics will include income, education, and employment. Data on socioeconomic characteristics will be available in Denmark and Sweden.

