8.3.4. Subgroups

Consistency for the primary endpoints and of the composite secondary endpoint will be evaluated among patients according to the following clinical or demographic characteristics:

- In each country (Denmark, Norway, Sweden)
- By age at OAC initiation (<65; 65-<75 years, ≥75-<85 years; and in patients ≥85 years if sample size permits)
- By sex (men and women)
- According to CHA₂DS₂VASc score category in the baseline
- According to CHADS₂ score category in the baseline
- According to HAS-BLED score category in the baseline
- According to initial dosage in the baseline (any licensed dose for AF vs reduced dose)
- In patients with/without chronic kidney disease (CKD) in the baseline

- In patients with/ without heart failure (HF) in the baseline
- In patients with/ without coronary artery disease (CAD) in the baseline
- In patients with/ without peripheral arterial disease (PAD) in the baseline
- In patients with/ without prior ischaemic stroke in the baseline
- In patients with/ without prior unspecified stroke in the baseline
- In patients with/ without prior haemorrhagic stroke in the baseline
- In patients with/ without prior TIA in the baseline
- In patients with/without prior systemic embolism at baseline
- In patients with/without prior gastrointestinal bleeding at baseline
- In patients with/without prior intracranial bleeding at baseline
- In patients with/without diabetes in the baseline

Depending on sample size, subgroup analyses for the primary and the composite endpoint may be repeated in some of the above subgroups with appropriate re-matching.

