8.7.2. Main analysis

To compare risks of the endpoints across the study cohorts, time to event analysis will be undertaken, using Cox proportional-hazards regression, with death as competing risk for endpoints not including death. Crude and adjusted HRs and 95% confidence intervals (CI) will be estimated for initiators of each NOAC. Follow-up will end on the date of a given endpoint, date of death (for non-death endpoints), date of discontinuation of or switch from the index OAC, date of emigration, or 31 December 2016, whichever comes first. A patient will be considered on-treatment from the date of the first dispensing of the index OAC and for the subsequent number of days corresponding to the number of tablets in all dispensed packages for rivaroxaban (used once daily) or half the number of tablets in all dispensed packages for dabigatran or apixaban (used twice daily) as long as there are no more than 30 days between the expiration and the start of the two adjacent dispensings. A discontinuation will be recorded as soon as 31 days elapse after the expiration of the number of days in a given dispensing (date of dispensing + days supplied + 31 days) in the absence of the next dispensing of the same OAC.

The approach to calculate the warfarin discontinuation date will be based on the median daily dose for all warfarin patients; this median daily dose will be used to calculate an end of supply date based on the dispensing strength and number of tablets in a package for each patient. Discontinuation will be assumed if there was no warfarin prescription within 30 days of the end date of the supply.

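### Clustering the pooled models on only three countries gives unreliable, usually too narrow, confidence intervals; country should be a stratum

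*Protocol*

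**What the plan says.** Section 8.7 fixes the role of country in the pooled analysis: "country will be used as a cluster variable to account for within-country correlation in the multivariate models". Section 8.7.2 then says of the Cox regression: "Crude and adjusted HRs and 95% confidence intervals (CI) will be estimated for initiators of each NOAC". Neither section names a variance estimator, a small-sample correction or degrees of freedom. Neither says that the baseline hazard is stratified by country or that matching is done within country.

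Three other statements bear on the point:

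- Section 8.7 plans country-specific results as well: "All analyses will be conducted on the combined patient-level dataset and on patient-level dataset stratified by country". Section 8.3.4 lists country as a subgroup.
- Section 8.3.3 lists the baseline covariates, beginning with "age at index date (in groups and as a continuous variable), sex, overall comorbidity". Country is not in the list.
- Section 8.7 defers the analytic strategy, "including variables for inclusion in the propensity score models, are described in the SAP". The absence of country from 8.3.3 therefore does not show that it is absent from the propensity score.

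**The concern.** A cluster-robust variance estimates uncertainty from the spread of cluster totals, so its reliability depends on the number of clusters and not the number of patients. Here there are three, and tens of thousands of patients do not help. A standard error built on two degrees of freedom is highly variable and typically too small.

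Country also does not behave like a sampling cluster in this study. Table 2 shows all the drugs in use in all three countries, so treatment varies within country. Country is a stratum and a potential confounder. Making it a variance cluster changes the standard error and leaves the point estimate as it was.

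At stake are the intervals of the pooled NOAC-warfarin contrasts to which the sentence applies. Section 6 gives the moderate precision of existing studies as a reason for this one, so apparent precision that is not real would undercut its purpose.

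**Working it through.** **The plan's own figure.** The protocol gives no figure that involves clustering. Its sample sizes come from the ordinary comparison of two independent proportions: for risk 0.02, RR 0.8, two-sided alpha 0.05 and power 0.80, the formula gives 17,341 per group against 17,307 in Table 3 (0.2% apart). They contain no allowance for clustering.

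**Step 1: coverage with three clusters.** Assume G = 3 equal clusters, an uncorrected sandwich variance and critical value 1.96. The cluster scores sum to zero, so the Wald statistic behaves as t(G-1) × √(G/(G-1)) = t(2) × √1.5. For t(2), P(|t| > x) = 1 - x/√(x² + 2).

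- Uncorrected: x = 1.96/√1.5 = 1.600, so P = 1 - 1.600/√(2.561 + 2) = 0.251. Coverage is 74.9%.
- With the G/(G-1) correction: x = 1.96, so P = 1 - 1.96/√(3.842 + 2) = 0.189. Coverage is 81.1%.
- With that correction and the t(2) critical value 4.303, coverage is restored. The multiplier becomes 4.303 × √1.5 = 5.27 instead of 1.96, an interval 2.7 times as wide as the uncorrected one.

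**Step 2: size of the standard error.** Under the same assumptions, the squared ratio of robust to model-based SE behaves as χ²(2)/3.

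- Median ratio: √(1.386/3) = 0.68.
- P(ratio < 1) = 1 - exp(-1.5) = 0.777.
- P(ratio < 0.5) = 1 - exp(-0.375) = 0.313.

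So the robust SE is too small in about 78% of cases and larger than the model-based SE in about 22%.

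**Step 3: simulation.** A Cox model was fitted to 18,000 patients followed for 1 year, with the sandwich variance summed over three countries and 1,500 replicates per row.

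| Country sizes | Yearly risk | Share treated | HR | Coverage, robust | Coverage, model-based | Median SE ratio | Robust SE smaller |
|---|---|---|---|---|---|---|---|
| 6,000 each | 3% | 50% | 0.8 | 76.8% | 95.6% | 0.70 | 76% |
| 4,000/4,000/10,000 | 3% | 50% | 0.8 | 74.5% | 95.6% | 0.64 | 83% |
| 4,000/4,000/10,000 | 3% | 50% | 1.0 | 72.0% | 95.1% | 0.63 | 82% |
| 6,000 each | 3/2.5/2% | 50% | 0.8 | 74.0% | 94.3% | 0.68 | 79% |

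The third row is a null effect, with type I error 1 - 0.72 = 28%. In these four rows the corrected t(2) interval covers 94-96%.

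A fifth, illustrative run gave the countries unequal treatment shares (60/55/35%) along with risks of 3/2.5/2%. A true HR of 0.80 was estimated as 0.85 on average. Robust coverage was 71% and model-based coverage was 92%. Neither variance repairs a point estimate that ignores country.

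**Step 4: possible confounding, only if country is not adjusted elsewhere.** Shares are the 2015 users in Table 2 (Denmark/Norway/Sweden):

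- Apixaban: 17,926/21,498/46,926 = 20.8/24.9/54.3%
- Rivaroxaban: 22,500/25,439/33,868 = 27.5/31.1/41.4%
- Dabigatran: 21,212/13,835/14,013 = 43.2/28.2/28.6%
- VKA: 87,851/69,212/188,966 = 25.4/20.0/54.6%

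The spurious factor is (drug shares × country risks)/(VKA shares × country risks). The country risks are assumed, each varied over 2%, 2.5% and 3%, the range that section 8.5 gives for the population as a whole. For dabigatran with risks 2/2/3%, the factor is 2.286%/2.546% = 0.90. With 3/3/2% it is 2.714%/2.454% = 1.11. Over all combinations:

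- Apixaban: 0.98 to 1.02
- Rivaroxaban: 0.95 to 1.05
- Dabigatran: 0.90 to 1.11

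**The case against.** The strongest reply is that the protocol does not commit to the procedure calculated above. It names no sandwich estimator, correction or reference distribution, and a t(2) interval with the correction would be valid. This stands as a limit on certainty. It does not rescue the plan: that valid version is very wide, and a random country effect or frailty would also be poorly estimated from three countries.

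Scope is also open. The sentence covers the multivariate models, while the main adjusted estimates come from propensity-score-matched samples and conventional covariate adjustment is a sensitivity analysis (8.7.3). A reader might infer that every pooled interval, including those for both primary endpoints, is certain to be wrong. The text does not settle that, since the sentence could be meant only for the regression-adjusted models. Nor are the intervals always too narrow: about one in five comes out wider than the model-based interval.

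A reader might also infer that country is left unadjusted and the pooled hazard ratios are confounded. The documents do not establish this, because the propensity-score variables are in the SAP. The dabigatran factor is the most extreme of the three contrasts, and apixaban's country mix is close to that of VKA. Table 2 counts users for any indication, not treatment-naïve NVAF initiators, and the country risks are assumed.

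Finally, country-specific analyses are planned, and they avoid both problems. They are separate results, however, and do not correct the pooled intervals.

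**Conclusion.** The variance choice in section 8.7 is wrong as written. Three countries cannot support a cluster-robust variance with a normal critical value. Nominal 95% intervals then cover about 75%, or about 81% with the G/(G-1) correction, and the median standard error is about 0.63 to 0.70 of the model-based one. The intervals are best described as unreliable and usually too narrow.

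These figures rest on reading the cluster variable as a sandwich variance, on a critical value of 1.96, and on a common hazard ratio across the countries. The analytic figures also assume equal clusters, but the simulation with unequal country sizes gave similar or slightly worse coverage. Adding country to the propensity score would not make the three-cluster standard errors valid.

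Confounding by country remains conditional on the SAP. If country is not handled there, the possible distortion is about 2% for apixaban, 5% for rivaroxaban and 10% for dabigatran, under the assumed risks and proxy shares.

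**What to change.** In section 8.7, delete country as a cluster variable and put in its place: *The pooled Cox models are stratified by country (country-specific baseline hazards), with model-based or matched-pair-robust standard errors.* State which pooled models this covers, including the propensity-score-matched analyses of the primary endpoints.

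Matching within country, or including country in the propensity score, is an acceptable complement. The country-specific hazard ratios already planned can then show whether the effects agree across countries.

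The cost is one sentence and one model option, using data already held. Exact matching on country, if chosen, may lose a few cross-border matches.

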8.7.1. Descriptive analysis

First, baseline characteristics (demographics, comorbidities, concomitant medications, risk factors, socioeconomic characteristics) of all patients included in the analysis will be described overall and by exposure cohort. Continuous variables (e.g., age, income) will be summarized using categories and/or means/medians as appropriate; categorical variables will be summarized using frequencies and proportions. Baseline characteristics both before and after propensity score matching (described below) will be presented.

For the primary and secondary endpoints, crude incidence rates and hazards ratios (HRs), and cumulative incidences (risks) over the follow-up period will be estimated in the four OAC cohorts.

8.7.2. Main analysis

To compare risks of the endpoints across the study cohorts, time to event analysis will be undertaken, using Cox proportional-hazards regression, with death as competing risk for endpoints not including death. Crude and adjusted HRs and 95% confidence intervals (CI) will be estimated for initiators of each NOAC. Follow-up will end on the date of a given endpoint, date of death (for non-death endpoints), date of discontinuation of or switch from the index OAC, date of emigration, or 31 December 2016, whichever comes first. A patient will be considered on-treatment from the date of the first dispensing of the index OAC and for the subsequent number of days corresponding to the number of tablets in all dispensed packages for rivaroxaban (used once daily) or half the number of tablets in all dispensed packages for dabigatran or apixaban (used twice daily) as long as there are no more than 30 days between the expiration and the start of the two adjacent dispensings. A discontinuation will be recorded as soon as 31 days elapse after the expiration of the number of days in a given dispensing (date of dispensing + days supplied + 31 days) in the absence of the next dispensing of the same OAC.

The approach to calculate the warfarin discontinuation date will be based on the median daily dose for all warfarin patients; this median daily dose will be used to calculate an end of supply date based on the dispensing strength and number of tablets in a package for each patient. Discontinuation will be assumed if there was no warfarin prescription within 30 days of the end date of the supply.

8.7.3. Sensitivity analysis

The following sensitivity analyses will be performed overall, for the primary endpoints and the composite secondary endpoint:

1. The intention-to-treat (ITT) like analyses: the overall comparative PS-matched analyses of the primary endpoints and the composite secondary endpoint will be repeated whereby patients in each OAC cohort will be followed from the index date until a given endpoint, death, emigration, or study end (no censoring by discontinuation or switching)
2. The overall comparative analyses of the primary endpoints and the composite secondary endpoint in the propensity score (PS)-matched analysis set will be repeated whereby the on-treatment time for patients treated with warfarin will be estimated based on a recently published methods using on maximum likelihood estimation of a parametric two-component mixture model for the waiting time distribution (52, 53). The algorithm found that 80% of current warfarin users will have presented themselves again for a refill after 91 days. A 30-day grace period will be added at the end of the 91 days
3. The overall comparative analyses of the primary endpoints and the composite secondary endpoint will be repeated in the full analysis dataset using conventional adjustment instead of PS matching
4. The overall comparative analyses of the primary endpoints and the composite secondary endpoint will be repeated in the full analysis dataset using conventional adjustment instead of PS matching
5. Analysis stratified on the initial dose will be performed after PS rematching within the initial dose defined strata.

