NOACs are recommended as first-line treatment strategy for stroke prevention in patients with AF by both United States (US) (11) and European (12) guidelines. However, national and sub-national payers in Europe are requiring data on comparative effectiveness and safety of OACs in routine clinical practice since the efficacy and safety achieved in the idealized clinical trial settings may not necessarily translate to routine practice because of the differences in the patient populations, the intensity of follow-up, and the variations in care that patients receive. The increasing interest in post-trial use of approved therapies and improved access to information on health care derived from multiple sources outside typical clinical research settings, including electronic health records, claims and billing data, product and disease registries, has led to a rapid growth in the field of real world evidence, including real world evidence on OACs. Key to understanding the usefulness of real-world evidence is an appreciation of its potential for complementing the knowledge gained from traditional clinical trials.

A number of observational studies have examined the safety and effectiveness of NOACs in real world settings, including both European and US studies. In three recent Danish cohort studies, NOACs and warfarin were associated with similar risks of ischemic stroke, but apixaban and dabigatran conferred lower risks of death (13) and bleeding (13-15). In a

Norwegian study, apixaban and dabigatran were associated with a lower risk of major or clinically relevant non-major bleeding than warfarin, with the exception of gastrointestinal bleeding, which was higher with dabigatran and rivaroxaban (16). Similar findings have been reported from the US, i.e., dabigatran, rivaroxaban, and apixaban were found to have similar effectiveness, but apixaban may be associated with a lower bleeding risk and rivaroxaban may be associated with an elevated bleeding risk (17). A Danish study of outcomes among patients treated with reduced-dose OACs found generally comparable rates of thromboembolic and bleeding events in all groups, noting a trend towards a higher rate of thromboembolic events associated with reduced dose of apixaban (18).

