7.2. Secondary objectives

- To compare risks of ischaemic stroke at an acute hospitalization with an overnight stay among the OAC-treatment naïve NVAF patients who initiate apixaban, dabigatran, rivaroxaban, or warfarin
- To compare risks of haemorrhagic stroke at an acute hospitalization with an overnight stay among the OAC-treatment naïve NVAF patients who initiate apixaban, dabigatran, rivaroxaban, or warfarin
- To compare risks of intracranial bleeding at an acute hospitalization with an overnight stay among the OAC-treatment naïve NVAF patients who initiate apixaban, dabigatran, rivaroxaban, or warfarin
- To compare risks of gastrointestinal bleeding at an acute hospitalization with an overnight stay among the OAC-treatment naïve NVAF patients who initiate apixaban, dabigatran, rivaroxaban, or warfarin

- To compare risks of acute myocardial infarction at an acute hospitalization with an overnight stay among the OAC-treatment naïve NVAF patients who initiate apixaban, dabigatran, rivaroxaban, or warfarin
- To compare risks of systemic embolism at an acute hospitalization with an overnight stay among the OAC-treatment naïve NVAF patients who initiate apixaban, dabigatran, rivaroxaban, or warfarin
- To compare all-cause mortality among the OAC-treatment naïve NVAF patients who initiate apixaban, dabigatran, rivaroxaban, or warfarin
- To compare risks of the composite endpoint of ischemic stroke at an acute hospitalization with an overnight stay, systemic embolism at an acute hospitalization with an overnight stay, acute myocardial infarction at an acute hospitalization with an overnight stay, or all-cause mortality among the OAC-treatment naïve NVAF patients who initiate apixaban, dabigatran, rivaroxaban, or warfarin
- To compare risks of any bleeding at an acute or planned hospitalization with an overnight stay among the OAC-treatment naïve NVAF patients who initiate apixaban, dabigatran, rivaroxaban, or warfarin
- To compare risks of any bleeding occurring at an acute hospital contact without an overnight stay among the OAC-treatment naïve NVAF patients who initiate apixaban, dabigatran, rivaroxaban, or warfarin
- To compare risks of bleeding (intracranial, gastrointestinal, other) recorded as the primary diagnosis at an acute hospitalization with an overnight stay among the OAC-treatment naïve NVAF patients who initiate apixaban, dabigatran, rivaroxaban, or warfarin (sensitivity analysis)

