8.2.1. Study population

The study population will be identified as treatment-naïve adults (aged 18 years or older on the index date) in the source population who have been diagnosed with non-valvular atrial fibrillation and initiated apixaban, rivaroxaban or dabigatran ('the NOACs') or warfarin between 01 January 2013 and 31 December 2016. Warfarin accounts for >98% of the vitamin K antagonists dispensed in the Scandinavian countries (Table 2). In the main analyses, patients will be followed from the index date until a given endpoint, death, OAC switching or discontinuation, emigration, or 31 December 2016, whichever comes first. In the sensitivity analyses of selected contrasts (an intention-to-treat like analysis), patients will be followed from the index date until a given endpoint, death, emigration, or 31 December 2016, whichever comes first.

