8.3.2.2. Secondary endpoints

- Ischaemic stroke at an acute hospitalization with an overnight stay
- Haemorrhagic stroke at an acute hospitalization with an overnight stay
- Intracranial bleeding at an acute hospitalization with an overnight stay
- Gastrointestinal bleeding at an acute hospitalization with an overnight stay
- Acute myocardial infarction at an acute hospitalization with an overnight stay
- Systemic embolism at an acute hospitalization with an overnight stay
- Death of all causes
- The composite endpoint of ischemic stroke at an acute hospitalization with an overnight stay, systemic embolism at an acute hospitalization with an overnight stay, acute myocardial infarction at an acute hospitalization with an overnight stay, or all-cause mortality
- Any bleeding at an acute or planned hospitalization with an overnight stay
- Any bleeding occurring at an acute hospital contact without an overnight stay

- Bleeding (intracranial, gastrointestinal, other) recorded as the primary diagnosis at an acute hospitalization with an overnight stay (sensitivity analysis)

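### All-cause mortality is a stand-alone secondary comparison, but every planned mortality estimate is on-treatment; no separate hazard ratio without censoring at treatment stop is planned

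*Protocol*

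**What the plan says.** Section 7.2 makes mortality an objective in its own right: "To compare all-cause mortality among the OAC-treatment naïve NVAF patients who initiate apixaban, dabigatran, rivaroxaban, or warfarin". Section 8.3.2.2 lists it separately from the composite of ischaemic stroke, systemic embolism, myocardial infarction and death.

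Section 8.2.1 sets main-analysis follow-up for all endpoints alike: "patients will be followed from the index date until a given endpoint, death, OAC switching or discontinuation, emigration, or 31 December 2016, whichever comes first". Section 8.7.2 repeats the rule; follow-up stops at the "date of discontinuation of or switch from the index OAC, date of emigration, or 31 December 2016, whichever comes first".

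The stop date is built in two ways in section 8.7.2. For NOACs it follows the tablets dispensed: "A discontinuation will be recorded as soon as 31 days elapse after the expiration of the number of days in a given dispensing". For warfarin, one median daily dose taken over all warfarin patients sets the end of supply, and discontinuation is assumed when no prescription follows within 30 days.

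Section 8.7.3 opens: "The following sensitivity analyses will be performed overall, for the primary endpoints and the composite secondary endpoint". Item 1 (ITT-like, no censoring at discontinuation or switch) and item 2 (warfarin time from a waiting-time model) each restate that restriction. The abstract gives the same scope, and section 8.2.1 speaks of the ITT-like analysis for selected contrasts.

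**The concern.** A patient whose health is failing may stop collecting a preventive drug, or be moved to another one, some time before death. Where that happens, censoring at treatment stop is not independent of mortality. If the pattern is the same in both arms the comparison may suffer little. If it differs, the on-treatment HR mixes a drug effect with a difference in who remains under observation.

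Three features of the protocol make an arm difference plausible. The stop-date rules differ, as described above. Section 8.9 concedes misclassification of treatment presence and timing, and says there is no information on warfarin dose. The same section says the severity of most comorbidities cannot be established, so baseline matching cannot be relied on to balance prognosis-linked stopping. The protocol describes no censoring weights or similar correction.

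What is at stake is the reading of the mortality result. The background reports from earlier Danish cohort work that "apixaban and dabigatran conferred lower risks of death", so the mortality HR is likely to be read closely. Under the present plan a reader could not see whether an on-treatment difference in deaths persists over full follow-up.

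**Working it through.** The documents state no figure on this point, so there is none to reproduce. The check is mainly a comparison of scope.

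| Planned analysis | Censors at stop or switch? | Separate mortality HR? |
|---|---|---|
| 8.7.1 rates, crude HRs, cumulative incidences | Yes; no other follow-up period is defined | Yes, on-treatment |
| 8.7.2 main Cox analysis | Yes | Yes, on-treatment |
| 8.7.3 item 1, ITT-like | No | No; deaths only within the composite |
| 8.7.3 item 2, alternative warfarin duration | Yes, with another warfarin stop date | No; deaths only within the composite |
| 8.7.3 items 3 to 5 | No change to the rule stated | No, under the lead-in |

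The checklist in Annex 2 remarks that both on-treatment and overall risks will be estimated. It names no endpoint, so it does not extend item 1 to mortality.

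**Is leaving treatment common enough to matter?** Section 6 cites 47% discontinuation over a mean of 416 days in US data. Under a constant hazard this is −ln(1 − 0.47) / (416/365.25) = 0.635 / 1.139 = 0.56 per person-year. It is reported regardless of drug, so it shows that stopping can be frequent and not that it differs by arm. The section also cites one-year switching to a VKA of 12%, 8% and 6% for dabigatran, rivaroxaban and apixaban. None of these figures is linked to prognosis.

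**When would bias arise?** The following illustration rests on assumed values, none taken from the protocol. A share s of each matched arm is frail. Death hazards are 0.25 per year (frail) and 0.03 (robust) in both arms, so the true HR is 1.00. The stopping hazard is 0.30 per year everywhere, except among frail warfarin patients, where it is 0.30 × k. The death hazard among those still on treatment at time t is

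h(t) = [s·0.25·e^(−(0.25+d)t) + (1−s)·0.03·e^(−0.33t)] / [s·e^(−(0.25+d)t) + (1−s)·e^(−0.33t)],

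with d the frail stopping hazard. For s = 0.2, k = 2, t = 1:

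- NOAC (d = 0.30): (0.1154 × 0.25 + 0.5751 × 0.03) / 0.6905 = 0.0668
- Warfarin (d = 0.60): (0.0855 × 0.25 + 0.5751 × 0.03) / 0.6606 = 0.0585
- Ratio at one year: 0.0668 / 0.0585 = 1.14

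Averaging log[h(NOAC)/h(warfarin)] over two years with log-rank-type weights gives the apparent HR:

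| Frail share | k = 1 | k = 1.5 | k = 2 | k = 3 |
|---|---|---|---|---|
| 10% | 1.00 | 1.04 | 1.08 | 1.15 |
| 20% | 1.00 | 1.06 | 1.11 | 1.22 |
| 30% | 1.00 | 1.06 | 1.12 | 1.24 |

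If the faster stopping is in the NOAC arm instead, the values are the reciprocals (1/1.04 = 0.96 to 1/1.24 = 0.81). If frail patients stop faster equally in both arms, the result stays at 1.00. No grace period is modelled separately. The table shows direction and mechanism and is not an estimate for this study.

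**The case against.** Several counter-arguments have force.

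- **Losing different shares of deaths by arm is not bias in itself.** Censoring removes person-time along with deaths. If 10% of both are lost in one arm and 20% of both in the other, the rate ratio is (0.90/0.90)/(0.80/0.80) = 1.00. This stands: bias needs stopping to be tied to prognosis, and differently by arm.
- **The documents show no such tie.** No section says that failing patients stop refilling, or that this differs between NOACs and warfarin. A reader might infer that the mortality HR will be biased; the documents support only that it could be. The grace period also keeps deaths soon after supply runs out, although none is stated for a switch.
- **Death is not absent from the checks.** Each death that is a patient's first composite event enters items 1 and 2, and item 2 varies the warfarin stop date directly. This stands, but a composite with three non-fatal components gives no mortality HR.
- **An ITT-like HR does not isolate the problem.** A gap between it and the on-treatment HR may be dilution by switching. This stands and belongs in the reporting.
- **Restricting sensitivity analyses limits their number.** The restriction is applied consistently, nothing is contradicted, and section 8.7 lets the SAP modify the plan. All true. Yet the protocol fixes this scope explicitly, so it is a choice open to comment and not a detail left for later.

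A reader might also infer that mortality is the endpoint at greatest risk. The documents do not rank endpoints in this way, and the other stand-alone secondary endpoints share the gap.

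**Conclusion.** The gap in scope is established by the text: mortality is compared as a stand-alone endpoint, every planned estimate of it is censored at discontinuation or switch, and both analyses that vary that rule stop at the primary endpoints and the composite. That this biases the mortality HR is not established. It would require prognosis-linked stopping or switching that differs by arm. The differing stop-date rules make that plausible, but the documents neither show nor quantify it. The range of 1.04 to 1.24 (or its reciprocals) holds only under the assumed hazards, with the excess stopping confined to one arm. The point is a worthwhile, inexpensive improvement and not an error in the main analysis.

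**What to change.** In section 8.7.3 item 1, add all-cause mortality to the endpoints analysed ITT-like, and align the lead-in and the abstract. Report the result beside the on-treatment mortality HR for each of the three NOAC-warfarin pairs, with a sentence stating that a difference between the two may reflect informative censoring or dilution by switching and that the comparison alone cannot separate them.

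The cost is three further Cox fits on matched sets that already exist. Table 1 already lists the population registers for death and emigration, and the ITT-like follow-up to 31 December 2016 is already defined in section 8.2.1. The drawback is that the ITT-like estimate is diluted by switching, which is why both should be shown. No primary analysis changes.
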